Orientation. One week prior to initiating the intervention, health coaches will conduct a home visit (~60 min) with each adult with AD/caregiver dyad in both intervention arms. Health coaches will deliver all necessary equipment and orient participants to the use of all equipment/software, answer questions regarding the general requirements of the trial, and demonstrate/practice the basic aerobic and resistance exercises with participants. Each dyad will be provided with the following: iPad®, iPod® touch, 2- Fitbit Versa Lites® and resistance bands (TheraBand, Akron, OH). The iPad® will be used to deliver either the real time exercise sessions (RGV only), individual support sessions, and for syncing the Fitbit of adults with AD. The iPod® will be used to sync the Fitbit of caregivers, as the iPad® is capable of syncing only one Fitbit. The iPod® will also allow for communication between the caregiver and the health coach via iMessage. Dyads in the RGV arm will be provided with an iPad®/HDMI adaptor, which allows video conference sessions to be displayed on a larger TV screen, if desired. All software/apps appropriate for each intervention arm will be loaded on the iPad®/ iPod®, i.e., Zoom®, Dropbox® (to provide access to recorded videos and written materials) and Fitbit app. Reminders regarding upcoming group video and/or health educator/dyad support sessions will be programmed using the iCalendar app on the iPad®. Access to non-study related materials, e.g., web browsing, app store etc. will be blocked on all iPads®/ iPods® until completion of the maintenance intervention (12 mos.). Individual support sessions. Dyads will be asked to attend 15-20-min education/support sessions (2 sessions/mo. during the active intervention (0-6 mos.) and 1 session/mo. during maintenance (7-12 mos.) delivered remotely on the iPad® using FaceTime®. No individual support sessions will be scheduled during the no-contact period (13-18 mos.). Sessions will be designed to educate and support the adult with AD and caregivers with meeting their 150 min/wk. goal for MPA. Each session will include a review of physical activity self-monitoring data, goal setting, strategies to increase and support MPA, and discussion of a topic relevant to MPA. During the active intervention (0-6 mos.) topics will include the importance of MPA for health and function, how to include MPA in the daily schedule, reduce barriers to physical activity, appropriate types of activity, creating a safe environment for physical activity, alternative activities for inclement weather, importance of hydration, etc. During maintenance (7-12 mos.) the discussion will focus on strategies to ensure continued participation in MPA, opportunities for physical activity in the community, and continued encouragement of dyadic activity. Topic outlines and information relative to support sessions will be pre-loaded on the iPad® where they can be assessed at any time across the 18-mo. trial. Self-monitoring-physical activity. Adults with AD and caregivers in both arms will be asked to wear a Fitbit Versa Lite activity tracker on their non-dominant wrist over the duration of the 18-mo. trial. This request may appear onerous; however, wearing the Fitbit is akin to wearing a wristwatch. Real-time data from the Fitbit is automatically transferred, via the web, to cloud storage (Fitabase, Small Steps Labs LLC, San Diego, CA), thus, participant burden is minimal. Fitbit data is available to both participants and the health coach via the Fitbit app. Immediate participant feedback of daily steps, minutes of sedentary time, and time spent in light, moderate and vigorous physical activity will be available via a graphic display on the device and the Fitbit app. The health coach will log into each participant account once per week to verify they are wearing and charging the device and to monitor participant activity solely for use in providing motivation and feedback during the individual support sessions. Outcome data for MPA and sedentary time will be assessed by accelerometer as described subsequently. Dyads will be reminded to wear and charge the Fitbit during group exercise (RGV only) and individual support sessions, and will receive automatic reminder messages every 3 days via the iPad® using the iCal app. We successfully used the Fitbit and these reminder procedures in our pilot trials in adults with AD (44) and similar procedures have been used by others (60).

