
RGV arm

Schedule. Group exercise sessions will be scheduled on 3 non-consecutive days/wk.(M,W,F) during the active intervention (0 to 6 mos.) and 1 day/wk. during maintenance (mos. 7-12). Group sessions will not be scheduled during the no-contact period (13-18 mos.). During orientation sessions, dyads will be asked to provide times of the day, between 10 a.m. and 7 p.m., that would be most convenient to complete the group sessions. Based on this information we will offer dyads in each cohort the choice between 2 potential session times each day. Prompts reminding adults with AD/caregivers of upcoming sessions will be sent using iMessage on the iPad® (adult with AD)/iPod® (caregiver) and iCalendar. Session delivery. Real-time exercise sessions will be delivered to adults with AD/caregiver dyads in their home by a trained health coach experienced in working with adults with AD using Zoom® video conferencing software. This software allows multiple users to see and interact with each other and the health coach via the iPad®. The health coach will conduct exercise sessions from our remote-delivery exercise studio (see facilities) which we used for remote delivery of exercise in our AD pilot (61) and in trials with adolescents with intellectual and developmental disabilities (IDD) (62), and adults with Down Syndrome (63). Tutorials describing trouble shooting for common technical problems with the Zoom® software, e.g., internet connectivity etc., will be loaded on the iPad®. Dyads with technical issues during the intervention may also contact research staff by phone or email. An alternative caregiver (other family member, staff etc.) may participate in the event that the caregiver enrolled in the trial is unable to attend an exercise session. These procedures were used in our AD pilot trial where alternative caregivers attended 8% of sessions (61). MPA session content. [name], a physical therapist, will develop the exercise program for this trial. He developed the exercise content for our pilot trial in adults with AD and has been involved in other exercise trials for adults with AD (R01AG034614, R01AG033673) (64-66). Each session will include a warm-up (~5 min), moderate intensity aerobic activity (3-5 METs) (~30 min), resistance and balance/coordination exercise (~5 min.), and cool-down/stretching (~5 min.). The MPA portion will ramp from 10 min/session at wk. 1 to the goal of 30 min/session at wk. 8. Each session will include aerobic activity, e.g., walking/jogging standing in place or sitting in a chair, sit to stand, dance movements; resistance exercise, e.g., TheraBand®-arm curls, leg extensions, side leg raises, and seated rows; and balance exercise, e.g. heel to toe walks, balance walk, and standing on one foot with/without support of a chair). [name] will provide modifications for participants having difficulty with any specific exercises. Health coaches will encourage interactions between participants during group sessions and ensure interactions between participants do not focus on dementia (67), but rather on issues relative to supporting their peer's efforts to increase MPA. Additionally, the Zoom app used for the sessions allows for messaging between participants during and after the group exercise sessions. Caregivers will be allowed to message the research staff and other caregivers for help and support both during the sessions and outside of the group sessions. We will keep copies of the messages sent to research staff on the KUMC P-Drive. Outside session MPA. Group exercise sessions will provide the potential to accumulate 90 min/wk. (3 sessions x 30 min/session) during the active intervention (0-6 mos.) and 30 min/wk. (1 session) during maintenance (7-12 mos.). Thus, MPA in addition to that accumulated in group sessions will be required to meet the MPA goal of 150 min/wk. To provide a transition from a sedentary to a more physically active lifestyle we will recommend goal of 45 min of MPA/wk. at wk. 1 and increase the goal by 15 min/wk.to reach the 150 min/wk. goal at wk. 8. We successfully used this MPA progression in previous trials in adults with AD (57). At the completion of each group session health coaches will provide a "weekly challenge" for participants to try a new activity or create and perform a new exercise routine etc. in order to reach the 150 min./wk. goal. Additionally, the NIA pamphlet "Exercise and Physical Activity: Your Everyday Guide" will be loaded on the iPad to assist participants in meeting the 150 min./wk. goal. Video recordings. Video recordings of all group exercise sessions will be uploaded to Dropbox®. Participants/caregivers will be encouraged to access video recordings using their iPads®/iPods® to assist with meeting the 150 min./wk. goal. Frequency and duration of participant/caregiver video access will be tracked using Dropbox® analytics. No contact follow up (13-18 mos.). Group video and individual support sessions will be discontinued. Participants will be

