demonstrate proper placement of the ActiGraphs at home visits scheduled at 0, 6, 12 and 18 mos. ActiGraphs will be distributed by mail for the 3-mo. assessment. Daily reminders to comply with the ActiGraph protocol will be sent to participant's iPad® each morning during the 7-day monitoring period. We have employed similar distribution and reminder protocols in previous trials (74 , 75-77, 79). Our current supply of ActiGraphs, plus the additional units requested in this proposal, will allow physical activity assessments to be completed on all participants in the proposed timeframe. Data collection. ActiGraphs will be initialized and downloaded using ActiLife Software version 6.13.3 or higher (ActiGraph Corp, Pensacola, FL) and set to collect in the raw data mode from all 3 axes at 60 Hz. Although the wGT3x-BT collects raw data from 3 axes, the widely used cut-points for determining activity intensity in adults proposed for this trial use acceleration data from the ActiGraph vertical axis (89). However, raw data from all 3 axes will be downloaded and stored, and will be available should algorithms for processing this data become available during this trial. Data processing Accelerometer data will be processed using the protocol for adults used in the 2003-2004 and 2005-2006 cycles of NHANES (89, 90). Data will be aggregated over 60-sec epochs. The following intensity cut-points will be used: sedentary (< 1.0 MET; ≤ 100 counts/min), light (1.1-2.99 METs; 101-2019 counts/min.), moderate (3.0-5.99 METs; 2020-5988 counts/min) and vigorous ≥ 6 METs; ≥ 5999 counts/min) (89, 90). Non-wear time will be defined as at least 60 consecutive minutes of zero counts, with allowance for 1-2 min of counts between 0 and 100. Counts ≥ 20,000/min will be considered spurious (91). All accelerometer data processing will be completed using custom SAS-/R programs developed by Drs. [name] and [name], the project statisticians, in collaboration with our research group. Missing accelerometer data. Recent advances in both statistical methods and computing power have made it possible to impute missing data with large data sets, such as will be collected in the proposed trial, i.e., 7 wk.-long assessments across 18 mos. A detailed description of the methods and procedures for handling missing ActiGraph data (non-wear and device malfunction time) is included in the analysis plan. MPA data for both adults with AD and caregivers will be analyzed including and excluding video conference exercise sessions (RGV arm).

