Statistical design. Baseline equivalence. The distributional properties of baseline demographic characteristics (MPA, BMI, age, sex, race/ethnicity, etc.) and dyadic relationship between adults with AD and their caregiver (quality, type, number of caregivers) will be inspected within the sample and between the RGV and EUC arms. Variables that demonstrate a significant nonequivalence between RGV and EUC arms will be statistically controlled in the hypothesis testing to improve accuracy of our inferences on intervention effects. Additionally, variables that significantly differ between dyads that dropped out and those that did not will be controlled to minimize any systematic bias stemming from attrition.

Primary aim: *To compare MPA (min/wk.) across the 6-mo. active intervention in adults with AD randomized to RGV and EUC.* Our analysis will account for/evaluate the clustering of observations (repeated measurements; level 1) within participants (level 2) and dyads (level 3; if multiple caregivers) by estimating intra-class correlations and variances/covariances of regression

coefficients at, and across, different levels in random-effects multilevel models (mixed models). To address the aim, models will examine overall between-arm difference in MPV across time (group effect), linear/non-linear change in MPV over time (time effect), and, if appropriate, between-arm difference in this change (group-by-time interaction), while controlling for (i) the number of contacts with research staff and (ii) the baseline characteristics imbalances between participant subgroups (RGV vs. EUC, dropouts vs. completers). For example, a significant interaction would indicate that adults with AD in the RGV arm achieve more minutes of MPA compared to those in the EUC arm and this difference becomes greater as intervention participation increases, i.e., in the later mos.

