Secondary aim: To compare adults with AD and their caregivers randomized to RGV or ECU on the following outcomes across 18 mos. *Adults with AD:* MPA (min/wk.), sedentary time (min/wk.), percentage meeting 150 min/wk. goal, functional fitness, activities of daily living (basic/instrumental), quality of life, residential transitions, neuropsychiatric symptoms, and cognitive function. *Caregivers:* MPA (min/wk.), sedentary time (min/wk.), functional fitness, quality of life, and caregiver burden. Similar mixed models will be fitted separately for these outcome variables to examine group effect, time effect, and group-by-time interaction while controlling for the number of contacts with research staff and the baseline characteristics imbalanced between participant subgroups.

Exploratory aim: To evaluate the influence of process variables/participant characteristics on MPA in adults with AD and their caregiver across 18 mos.: age, sex, BMI, attendance (exercise/support sessions), use of recorded sessions, PA self-monitoring, peer interactions during group sessions, caregiver support, type and quality of the dyadic relationship, number of caregivers, and level of dementia. If MPA is not significantly different between RGV and EUC across 18 mos., i.e., no significant group effect or group-by-time interaction, we will combine the two arms and examine associations of the process variables/characteristics with MPA in mixed modeling. However, if a significant between-arm difference in MPA is identified, we will determine whether the process variables/characteristics enhance or attenuate the treatment effects, i.e., moderation, by testing a 2-way interaction with the group effect and/or a 3-way interaction with the group-by-time interaction term. In addition, we will examine how caregiver MPA influences the MPA of adults with AD over the 6-mo. active intervention, 6 mos. maintenance, and 6 mos. no contact. Some variables will be measured only at baseline, some will be summarized across the trial, while others will be assessed at specific time points. Thus, we will carefully design our models to assure the appropriateness of the analysis.

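### The primary and secondary models adjust for an undefined, post-randomisation count of staff contacts, and no arm comparison without it is planned

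*Combined protocol and SAP*

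**What the plan says.** Section V.A (Statistical and Data Analysis, Primary aim) sets out to compare activity "across the 6-mo. active intervention in adults with AD randomized to RGV and EUC". The mixed model estimates a group effect, a time effect and, if appropriate, their interaction, "while controlling for (i) the number of contacts with research staff". Baseline imbalances are listed separately as item (ii), so the contact count is not presented as a baseline variable. The Secondary aim paragraph carries it into every secondary model: "while controlling for the number of contacts with research staff and the baseline characteristics imbalanced between participant subgroups".

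The Exploratory aim uses the 18-month result as a switch. If there is "no significant group effect or group-by-time interaction, we will combine the two arms" and study the process variables in the pooled sample.

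The scheduled contacts are as follows.
- RGV only: "Group exercise sessions will be scheduled on 3 non-consecutive days/wk.(M,W,F) during the active intervention", then one a week in months 7-12.
- Both arms, individual support sessions: "2 sessions/mo. during the active intervention (0-6 mos.) and 1 session/mo. during maintenance (7-12 mos".
- Both arms: research staff "demonstrate proper placement of the ActiGraphs at home visits scheduled at 0, 6, 12 and 18 mos".
- Unscheduled: technical calls and emails (RGV arm, Session delivery) and messages to research staff (described for both arms).

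The analysis is called intent-to-treat under Missing data, and the design is so called in the monitoring text on participant compliance.

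**The concern.** Assignments are revealed at the orientation session, before the intervention starts, so intervention contacts accrue after randomisation and may depend on arm. Conditioning on such a variable need not estimate the effect of assignment. It can remove part of the benefit, and it can bias the contrast when contact and activity share a cause.

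Three readings are open: (1) all contacts, including the group sessions that exist only in RGV; (2) only contacts scheduled alike in both arms, namely support sessions or assessment visits; (3) unscheduled messages and technical calls. The plan also does not say whether the count is one total per person or varies over time.

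The primary group test is at stake. Under one reading it is untouched, and under another it has almost no power. The choice would be left to the analyst. The analysis of activity with and without video sessions (Assessments, Missing accelerometer data) changes the outcome and not the covariates, so it supplies no unadjusted comparison.

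**Working it through.** **Inputs from the documents.** Difference 10 min/d, SD 30 min/d, correlation 0.22, 21 measurements, at least 42 per arm (section C, Sample size). Pilot attendance 77% at group sessions (adults with AD) and 87% at support sessions; pilot Fitbit-wear SD 27.7 points in adults with AD (Background, Potential for video conferencing).

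**Assumptions.** Two-sided alpha 0.05; 26 weeks per six months; SD 30 is a single-day SD; constant effect at months 3 and 6; between-person SD of attendance s = 0.15 to 0.277. The upper value borrows the Fitbit-wear SD.

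**The plan's own power.** λ = f²·N·m/(1+(m−1)ρ) = (10/60)² × 84 × 21/(1 + 20 × 0.22) = 49/5.4 = 9.07. On 1 and 82 df this gives 84.5% (85.9% with f = 0.17), so the stated 80% or more is met without the covariate.

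**Scheduled contacts.** Months 0-6: RGV 3 × 26 + 2 × 6 = 90; EUC 12. Months 0-18: RGV 90 + 26 + 6 = 122; EUC 12 + 6 = 18.

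**Group effect, no covariate.** This uses the 14 post-baseline days (months 3 and 6) instead of 21 measurements. Person-mean SD = 7 × 30 × √(0.22 + 0.78/14) = 110 min/wk. SE = 110.3 × √(2/42) = 24.1. Power for 70 min/wk is 82%.

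**Reading (1), attended contacts.** Arm difference d = 0.77 × 78 = 60. Pooled within-arm variance w = [(78s)² + 2(12s)²]/2. VIF = 1 + (d²/4)/w. At s = 0.20, w = 127.4 and VIF = 1 + 901.8/127.4 = 8.08.

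| s | Variance of count explained by arm | SE multiplier | SE (min/wk) | Power |
|---|---|---|---|---|
| 0.15 | 93% | 3.69 | 89 | 12% |
| 0.20 | 88% | 2.84 | 68 | 17% |
| 0.25 | 82% | 2.35 | 57 | 23% |
| 0.277 | 79% | 2.17 | 52 | 26% |

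The multiplier does not depend on the outcome SD, the correlation or the effect size. The 18-month counts (104 group, 18 support) give 3.66 to 2.16.

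This power column assumes that benefit does not depend on attendance. Simulation on the post-baseline mean (4000 runs per setting) gave 12-27% in that case. It gave 7-10%, with an estimate of 35-38 min/wk, if half the benefit is proportional to attendance. If all of it is, rejection is about 5% and the estimate 1-5 min/wk against a true 70. A random-intercept mixed model (2000 runs, up to 15% of days missing) agreed: SE 24-24.5 and power 81-82% without the covariate, SE 52-92 and power 12-27% with it. If scheduled rather than attended contacts are counted, the count is an exact function of arm and the two effects cannot be separated.

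**Bias from a shared cause.** In a separate simulation (attendance SD about 20 points, all contacts counted), none of a true 10 min/d effect ran through attendance, but attendance and activity shared a cause (assumed correlations 0.5 and 0.3). The adjusted estimate was about 1.0 min/d; without the covariate it was about 10.

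**Reading (2).** Support sessions only: SE about 24, estimate 69-70 min/wk, power 80-82%. Assessment home visits give the same count for every completer and so have no effect among completers.

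**Reading (3).** The documents give no figures from which to size it.

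**If SD 30 is the SD of a week's daily mean.** SD = 7 × 30 × √(0.22 + 0.78/2) = 164 and SE = 35.8. Power of about 49% becomes 8-14% under reading (1).

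**Group-by-time (three waves, simulated).** Power is 95-97% without the covariate, with one total per person, or with support sessions only. With all contacts time-varying and benefit not dependent on attendance, it is 20-47% (contacts per interval) or 77-82% (cumulative). With proportional benefit it is about 5% or 60-68%.

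**The case against.** The strongest reply is that every large figure comes from reading (1), which the text does not favour. Sessions are delivered by the health coach. Research staff distribute accelerometers and take calls and messages, and copies of those messages are kept. The blinding paragraph separates unblinded coaches from blinded research assistants. Session exposure is called attendance and already appears as an exploratory process variable. This stands: usage leans towards (2) or (3). It remains inference, because the analysis section does not define the term. The text on the last phase, "No contact follow up (13-18 mos.). Group video and individual support sessions will be discontinued", gives reading (1) some support, but it is only a phase label and research-staff home visits continue within it.

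The power loss also rests on an attendance SD that the documents do not give. At 35 points the formula above gives 70% of variance explained and 35% power. A variant with 21 measurements, SDs of 10-35 points and group and support attendance moving together gives 10-43%. The size is therefore uncertain; the direction is not.

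Third, dropping a prognostic covariate that arm does not affect costs precision, and the documents give no correlation. With SE multiplied by √(1 − r²), power with the covariate would be 85% at r = 0.3, 88% at 0.4, 91% at 0.5 and 95% at 0.6. Deletion would thus forgo 3 to 13 points, but it only returns power to the 82% computed without the covariate.

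Fourth, group-by-time is unaffected by a single total per person, and that test can still prevent pooling in the exploratory analysis. This is right. It limits the damage but does not protect the group effect.

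**Conclusion.** The concern holds. The models condition on an undefined count that accrues after randomisation, and no arm comparison without it is planned. That departs from the stated intent-to-treat comparison whichever definition is meant. This part is certain from the text, apart from the timing of the count, which is inferred from the schedule.

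The numerical consequence is conditional. The test is essentially unchanged if the count covers only contacts scheduled alike and unaffected by arm. Power is about 12-27%, or as low as 5%, if attended group sessions count, under the assumed attendance SDs of 15-28 points. The effect cannot be sized for unscheduled contacts. The same covariate affects every secondary model, and the group-effect part of the pooling rule inherits the problem. An undefined term should not be able to move the primary test this far, so it should be corrected before analysis.

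**What to change.** Delete the contact count from the primary and secondary models in section V.A, so that the arm contrast does not condition on a variable that assignment can change. If attention or dose is of interest, state which contacts count, over which window, and whether the count is one total or time-varying. Then report that contact-adjusted model as a labelled sensitivity or exploratory analysis. Defining the count while keeping it in the primary model is not enough, because a defined count that arm can change still does not give the effect of assignment.

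The change is to SAP wording only, with no new data or visits. The precision given up is about 3 power points at an assumed r = 0.3, and more if the count is strongly prognostic and unaffected by arm. The resulting 82% still meets the plan's stated 80%, with SD 30 read as a single-day SD.

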BMI. Weight will be measured in duplicate in light clothing on a calibrated scale (Model #PS6600, Belfour, Saukville, WI) to the nearest 0.1 kg. Standing height will be measured in duplicate with a portable stadiometer (Model #IP0955, Invicta Plastics Limited, Leicester, UK). BMI will be calculated as weight (kg)/height (m²). Session attendance for group exercise (RGV only) and support sessions will be obtained from records maintained by the health coach, and expressed as the percent of possible sessions from 0-6 mos. and 7-12 mos. Attendance for adults with AD, enrolled caregivers, and alternative caregivers will be recorded separately. Use of recorded videos (frequency and duration of access, RGV only) will be assessed using Dropbox® analytics. Self-monitoring of physical activity will be assessed as the percentage of days with Fitbit data over a minimum of 8 hrs., between 6 am and midnight (0-6, 7-12, 13-18 mos.). Peer interactions (RGV only). Staff will review video recordings of a random sample of 33% of group exercise sessions to identify and classify both peer to peer, and health coach to participant interactions. Interactions will be quantified and coded as verbal/non-verbal (waving, pointing, shaking head in agreement/disagreement), and as positive, neutral or negative, relative to support, using a modification of a checklist we previously developed for a group video exercise intervention for adolescents with IDD (62). Caregiver support will be assessed using the percentage of group exercise sessions (RGV) and/ or individual support sessions completed by both the person with AD and their caregiver. Quality of the dyadic relationship will be assessed at baseline, 6, 12, and 18 mos. using the dyadic relationship scale (DRS) which measures negative and positive dyadic interactions from the perspective of both the patient and the caregiver. The DRS has acceptable construct, discriminant, and concurrent validity, as well as reliability for both patients and caregivers(105). We will evaluate the impact of the DRS on our primary and secondary outcomes as well as examine changes across time in both groups. Type of dyadic relationship. We will document the type of caregiver, e.g., spouse, adults child, paid staff, and evaluate the impact of caregiver on our primary and secondary outcomes. Number of caregivers. We will document the number of different caregivers for adults with AD and evaluate the impact of the number of caregivers on our primary and secondary outcomes. Level of dementia will be assessed at baseline using the CDR(110) which has shown acceptable validity(111) and reliability(112). Energy Expenditure of Remote Sessions Energy expenditure of the remote sessions will be assessed in a volunteer sample of both patient and caregiver using a previously validated portable, open-circuit indirect calorimeter (Cosmed, Italy) which measures breath-by-breath ventilation, expired oxygen, and carbon dioxide. Study staff will schedule the assessment with participants which will involve an

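### The exploratory MPA analysis is chosen by a significance test: a non-significant result pools the arms with no statement that arm stays in the model, and moderation is described only after a significant one

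*Combined protocol and SAP*

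**What the plan says.** The rule is in Section V.A, under the Exploratory aim. Its trigger is "If MPA is not significantly different between RGV and EUC across 18 mos., i.e., no significant group effect or group-by-time interaction". When that holds, "we will combine the two arms and examine associations of the process variables/characteristics with MPA in mixed modeling". The other branch reads "if a significant between-arm difference in MPA is identified, we will determine whether the process variables/characteristics enhance or attenuate the treatment effects", to be done through two-way interactions with group and three-way interactions with group-by-time. The paragraph does not say whether arm is kept or removed in the combined analysis. It ends with a general assurance: "Thus, we will carefully design our models to assure the appropriateness of the analysis".

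The variables to be studied are a mixture. Age, sex, level of dementia and baseline BMI are fixed before randomisation. Others arise afterwards, and the Exploratory outcomes section ties several of them to one arm: "Session attendance for group exercise (RGV only) and support sessions", "Use of recorded videos (frequency and duration of access, RGV only"), and "Peer interactions (RGV only"). Caregiver support is a percentage of sessions completed jointly. It draws on group exercise and/or support sessions in RGV, whereas EUC has support sessions only.

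**The concern.** Two things depend on which side of the significance threshold the MPA comparison falls.

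The first is pooling. A non-significant difference in a trial of this size is compatible with a real one. If the arms are combined and arm is not in the model, a process variable that is higher in RGV by design acts partly as a proxy for arm. It can then show an association with MPA that has nothing to do with the process itself.

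The second is moderation. A characteristic can modify the effect of RGV without any significant average effect, and as described the plan would not look for this.

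The practical stake is interpretation. The Rationale presents RGV as something community agencies might adopt, so which components appear to drive MPA, and for whom, will be read with interest even though the aim is exploratory.

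**Working it through.** **Inputs.** From Section C (sample size): 42 per arm after attrition, about 20% attrition, correlation 0.22, 21 and 35 measurements, 10 min/d with SD 30 (f=0.17) for months 0-6, and f=0.15 with the example 6 ± 30 min/d for later months. Taking 20% off 50 per arm leaves 40, so both 42 and 40 are used. Assumed: two-sided alpha 0.05 (none is stated), and 35 measurements for the 18-month comparison (five assessments × 7 days).

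**Power.** With noncentrality λ = f²·N·m / (1+(m−1)ρ) and a noncentral F on 1 and N−2 degrees of freedom:

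- Plan's active phase: 0.17²·84·21 / (1+20·0.22) = 50.98/5.4 = 9.44, power 86%. This agrees with the stated figure of at least 80%.
- Plan's later phase, f=0.15: 0.0225·84·35 / (1+34·0.22) = 66.15/8.48 = 7.80, power 79%. With N=80, λ=7.43 and power is 77%. The plan states at least 81%.
- The example in the same sentence: f = 6/(2·30) = 0.10, not 0.15; f=0.15 would be 9 min/d. At f=0.10, λ = 29.4/8.48 = 3.47 and power is 45%; with N=80, λ=3.30 and power is 43%.

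On the group effect alone, the arms would therefore be pooled in about 55% of trials if the true difference is 6 min/d, and in about 21-23% if it is 9 min/d.

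**Bias when arm is absent.** The SD of a participant's mean is 30·√(8.48/35) = 14.77 min/d. Suppose a process variable has no effect within arm but its mean differs by g SD between arms. The slope without arm is then about Δ·g/(4+g²), where Δ is the observed arm difference in MPA. For Δ=6 and g=2 this is 12/8 = 1.5 min/d per SD. Trials that reach the pooled branch have smaller observed differences, so the average there is lower.

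Simulation on participant means (42 per arm, 40,000 trials per row, analysed only when the group effect is non-significant):

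| True difference (min/d) | Arm gap g (SD) | Pooled | Mean slope, no arm | False associations, no arm | With arm |
|---|---|---|---|---|---|
| 0 | 2 | 95% | 0.0 | 3.5% | 4.8% |
| 6 | 1 | 55% | 0.8 | 6.5% | 5.3% |
| 6 | 2 | 55% | 0.9 | 7.8% | 4.9% |
| 6 | 4 | 55% | 0.7 | 7.9% | 4.9% |
| 9 | 1 | 21% | 0.9 | 7.9% | 5.0% |
| 9 | 2 | 21% | 1.2 | 10.8% | 4.9% |
| 9 | 4 | 21% | 0.9 | 11.4% | 4.8% |

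With 40 per arm the ranges are 6.3-7.9% at 6 min/d and 7.3-11.9% at 9 min/d. A separate set of 4,000 trials per setting reached 14% for standardised arm effects up to 0.66, that is up to 0.66·14.77 = 9.7 min/d. With arm in the model the mean slope is about zero throughout.

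**RGV-only variables.** Group-session attendance, recorded-video use and peer interactions have no EUC value. The pooled branch needs a coding rule that the plan does not give. In the other branch, an interaction of such a variable with arm cannot be estimated. Coding them as zero in EUC (g=2 within RGV) gives about 8% false associations at 6 min/d and about 12% at 9 min/d.

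**Moderation gate.** For a balanced binary moderator (42 per arm, 6,000 trials, assumed subgroup effects), the interaction is detected as follows:

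| Subgroup effects (min/d) | Tested always | Tested only after a significant group effect |
|---|---|---|
| +10 / −10 | 86% | 2% |
| +16 / −4 | 87% | 31% |
| +12 / 0 | 45% | 18% |

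**The case against.** The case for leaving the plan alone has real content.

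- **The plan never says arm is removed.** A reader might infer that from the wording about combining the arms, but the text supports only the narrower statement that retention is not specified. The closing promise of careful model design is compatible with keeping arm, although it commits to nothing.
- **Not every variable is exposed.** A reader might infer that all the listed variables are confounded with arm. Age, sex, dementia level and baseline BMI are balanced in expectation by randomisation. Support-session attendance is a percentage of a schedule that is the same in both arms, so it has no built-in gap. Number of staff contacts is a covariate in the primary and secondary models, not a listed process variable.
- **The worst figures do not coincide.** Pooling in more than half of trials belongs to 6 min/d, where false associations stay at or below about 8%. Rates of 11-14% belong to 9 min/d or slightly more, where pooling occurs in about a fifth of trials. The arm gaps of 1-4 SD are assumed; at 0.5 SD the rate is only 5-6%.
- **The gate is wider than simulated.** A significant group-by-time interaction also prevents pooling, and 10 min/d is anticipated in months 0-6. Pooling would then be somewhat less frequent than shown.
- **Gating moderation limits subgroup searching** in a trial of about 40 per arm, and the documents nowhere hypothesise opposite effects. The +10/−10 row is an extreme illustration.

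All of this reduces the size of the problem. It leaves in place a rule that treats non-significance as grounds for pooling, the silence on arm, and the lack of any workable analysis across both arms for the RGV-only variables.

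**Conclusion.** The point holds in limited form. The plan lets a significance test select the exploratory model and does not say that arm is retained when the arms are combined. For caregiver support and the RGV-only variables, omitting arm would credit part of any undetected arm effect to the process variable. The excess over the nominal 5% is roughly 1 to 3 percentage points at 6 min/d. At 9 min/d or slightly more it is about 2 to 9 points, in a branch then entered much less often. With no true arm difference there is no upward bias.

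Making moderation conditional on a significant difference also loses power to find it, by an amount that depends entirely on the assumed subgroup effects.

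The figures rest on two-sided alpha 0.05, the plan's SD and correlation, assumed arm gaps, and a gate simplified to the group effect. A reader might infer that the trial's main conclusions are at risk. They are not: the primary and secondary analyses do not pass through this rule. This is a correction worth making to an exploratory section, not a threat to the trial.

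**What to change.** Amend the Exploratory aim in Section V.A to say that:

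1. Arm and arm-by-time stay in every exploratory model that covers both arms, whatever the p-value of the MPA comparison.
2. Group-session attendance, recorded-video use and peer interactions are analysed within the RGV arm only.
3. Moderation by a short prespecified list of baseline characteristics is examined regardless of the main result. Estimates and confidence intervals are reported as exploratory, and the number of interactions tested is stated.

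The cost is a few sentences of text, one or two degrees of freedom per model, and a few additional interaction tests that need cautious interpretation with multiplicity in mind. No new data are needed. While editing, reconcile the f=0.15 label with the 6 ± 30 min/d example in Section C, because the two imply very different chances of entering the pooled branch.
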